9.4.4 Exploratory Analyses/Assessments

- CTC levels: Baseline level of CTC (detectable or undetectable) will be compared to proportion with TTP at 6 months to determine if there is an association using Fisher's Exact tests. Change in CTC levels (increase or decrease) after 1 and 2 cycles will be compared to proportion with TTP at 6 months to determine if there is an association using Fisher's Exact tests. Markers of mTOR pathway activation: Descriptive statistics will summarize the IHC parameters of staining intensity, percentage positivity, distribution, and intracellular localization for each protein. Due to possible limited specimen quantity, IHC outcomes will be dichotomized. Activation will be measured by % positive cells and intensity using published IHC cutpoints for high/low: cytoplasmic pAkt > 40% or 2-3+, cytoplasmic PTEN intensity < 10% or 0-1+, cytoplasmic pS6RP > 70% or 2-3+, or LKB1 0-1.⁷⁻¹² Univariate analysis using Cox's model will be performed to test whether the dichotomized expression of each protein using the published cutpoints is a significant predictor of TTP. Results for each test will include the hazard ratio (HR) with 95% confidence intervals. The association between each protein and the two binary coding schemes for AFP decline ($\geq 50\%$ or $\geq 20\%$) on C2D1 will be tested using Fisher's exact test. Results for each test will be summarized with proportions with pathway activation and 95% confidence intervals for each AFP subset. Each patient will also be categorized as having overall mTOR pathway activation (defined as any combination of high pAKT, high pS6RP, low PTEN, and/or low LKB1) or not. This binary variable will also be examined for its relationship with TTP, OS, AFP response, and other clinical endpoints using the same methods described above. For each test of association with AFP change, based upon Fisher's exact test large differences can be detected (e.g. 10% among 7 patients with marker-low, 80% among 8 patients with marker-low) (power=81%, $\alpha_2=10\%$). The sample size is too small to test for a difference in TTP, OS, or other clinical endpoints according to pathway activation status. The expected sample size will be ≥ 25 cases (expect 40 to 45 cases) with IHC-quality archival tumor, with the expectation that $\sim 75\%$ of cases will be evaluable for TTP ($n \geq 18$) and 60% evaluable for AFP response on C2D1 ($n \geq 15$).

Genotype findings will be dichotomized as presence or absence of any mTOR pathway aberration or combination thereof (e.g. mutations in AKT, mTOR, PTEN, PIK3CA, and/or TSC1/2). This binary variable will be examined for its relationship with time to progression, overall survival, AFP response, and other clinical endpoints by univariate analysis using Cox's model. Concordance between primary and metastatic specimens on mutational profile will be described individually due to small sample size. Other tumor genotype findings and relationship to clinicopathologic covariates will be reported descriptively.

To optimize sample size and ensure adequate number of evaluable cases, these analyses of mTOR pathway IHC and genotype markers will also be performed on cases and samples CC#09455 when available, to ensure at least 25 evaluable cases with adequate archival tumor for testing. Although pooling of data and specimens across studies introduces potential confounding, it is appropriate for these exploratory analyses as the eligibility criteria and protocol therapy were overlapping for CC#09455 and the current study.

- Hepatitis B viral load: In all patients with active HBV infection, changes in HBV DNA quantitative by PCR (conversion from undetectable at baseline to detectable on study or an increase by $\geq 50\%$ from baseline versus unchanged from baseline) will be characterized using descriptive statistics (mean, median, standard deviation, and 95% confidence interval) to calculate the proportion of patients with an increase in viral load while on protocol therapy.
- Future biomarker research on banked specimens will be reported outside of the main study report

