1.4.2 Enumeration of Circulating Tumor Cells in HCC

Circulating tumor cells (CTC) will also be enumerated in patients in this study. In the majority of carcinomas, tumor cells have been detected in peripheral blood from patients by using the CellSearch System (Veridex LLC). (Allard, Matera et al. 2004) In breast and colon cancer, CTC levels convey prognostic information, correlating with PFS and overall survival; changes in CTC levels on treatment may also predict response to chemotherapy. (Cristofanilli, Budd et al. 2004; Cohen, Punt et al. 2008; Dawood, Broglio et al. 2008) In a study of 20 patients with locally advanced or metastatic hepatocellular carcinoma, CTC were detected using the CellSearch system in 9 patients (45%). (Zee BC 2007) Preliminary results from a pilot study at UCSF of 20 patients with metastatic HCC show approximately 30% to have ≥ 3 CTC/7.5mL and 47% to have ≥ 1 CTC/7.5 mL detected, while none of 10 control patients with non-malignant liver disease had detectable CTC ([name], unpublished results). A novel slide-based circulating epithelial cell assay (CEpiC) has also shown the ability to detect circulating tumor cells in patients with epithelial tumors including HCC (personal communication, [name], The Scripps Research Institute). (Cho, Wendel et al. 2012; Wendel, Bazhenova et al. 2012) Among 5 patients treated in the PK expansion cohort of the UCSF-Northwestern phase I trial of temsirolimus plus sorafenib in advanced HCC, all 5 had detectable circulating epithelial cells by the slide-based CEpiC assay ([name], unpublished data). Portal vein tumor invasion is a negative prognostic factor in HCC, and multiple studies have shown that tumor invasion or tumor thrombosis of the portal vein is a reliable predictor of shorter survival. (Tanaka, Tobe et al. 1989; Giannelli, Pierri et al. 2002) This suggests that tumor cells within the vasculature (such as are measured by CTC testing) may also be prognostic. Along with the preliminary data showing detectability of CTC in HCC patients treated on the phase I trial of this treatment regimen, these data provide the rationale to further explore CTC levels as a potential biomarker in the current phase II study.

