2.3 Exploratory Objectives and Other Assessments

- TTP, RR, PFS, OS, TTF, AFP response, and toxicity and tolerability will be described in subsets defined by HBV, HCV, Asian, and non-Asian status.
- To enumerate CTC at baseline and after 1 and 2 cycles of therapy to evaluate for any relationship between baseline levels and change in levels with median TTP and/or OS
- To characterize baseline mTOR pathway activation by immunohistochemistry (IHC) for selected markers such as pS6RP, pAKT, PTEN, and LKB1, and by tumor next-generation DNA sequencing of targeted genes including mTOR pathway in archival tumor specimens from HCC patients treated with temsirolimus plus sorafenib.
- To examine the relationship between baseline mTOR pathway activation by IHC and by sequencing and clinical outcomes on treatment with temsirolimus plus sorafenib.
- In patients with chronic active HBV infection or exposure, to monitor hepatitis viral load during and after therapy with an mTOR inhibitor
- To bank peripheral blood specimens and left-over archival pathology or cytology specimens for future research

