7.3.1 Circulating Tumor Cell Measurements

CTC will be enumerated using a novel slide-based assay (CEpiC) at baseline and on Day 1 of Cycles 2 and 3 (up to 7 days before treatment date). The slide-based circulating epithelial cell assay (CEpiC) is a new methodology to identify circulating epithelial cells and credential them as tumor cells. In the assay, each tube of approximately 7.5 mL (0.5 TBS) of anti-coagulated peripheral blood is lysed and all mononuclear cells are plated on cell adhesion glass slides. After appropriate pre-processing, the monolayer is incubated with a pan-anti-cytokeratin antibody and subsequently with a secondary fluorescent antibody. The samples are also stained with the nuclear stain DAPI. Slides are then analyzed with an automated digital microscope and data analyzed and correlated. The analysis predominantly consists of a cytometric and morphologic correlation that identifies intact cells that have a cytoplasmic cytokeratin stain consistent with epithelial cells. Controls include identically processed normal donor blood and sub-sampling of the patient blood excluding the primary antibody. The result of the CEpiC assay is the count of positive CEpiCs per milliliter of peripheral blood with associated imagery. CTC testing and analysis will be performed in the laboratory of [name]., at the Scripps Research Institute, with the assistance of the clinical coordinator, [name]. CTC testing will be performed without knowledge of the patients' clinical status.

Please see Study Laboratory and Procedures Manual for instructions regarding the collection, shipping, and handling of blood specimens for the CEpiC assay.

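### Baseline CTC is tested only as detectable or undetectable, which is likely to leave too few undetectable patients for an informative test, although the assay gives a count

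*Combined protocol and SAP*

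**What the plan says.** The exploratory CTC objective (2.3, repeated in 2.4.3) is framed in terms of levels. Its aim is to "evaluate for any relationship between baseline levels and change in levels with median TTP and/or OS".

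The measurement is described in 7.3.1: "CTC will be enumerated using a novel slide-based assay (CEpiC) at baseline and on Day 1 of Cycles 2 and 3". The same section gives the form of the output: "The result of the CEpiC assay is the count of positive CEpiCs per milliliter of peripheral blood".

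The analysis in 9.4.4 reduces baseline CTC to two groups: "Baseline level of CTC (detectable or undetectable) will be compared to proportion with TTP at 6 months". The stated purpose is "to determine if there is an association using Fisher's Exact tests". Change after 1 and 2 cycles is analysed separately, as increase or decrease against the same 6-month outcome. The section gives no threshold for detectability, no cutpoint for the count, no fallback if nearly all patients are positive, and no CTC analysis of OS.

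The background in 1.4.2 reports earlier experience with this assay in the same disease and regimen. Among 5 patients in the phase I pharmacokinetic expansion cohort, "all 5 had detectable circulating epithelial cells by the slide-based CEpiC assay". It also cites 9 of 20 HCC patients (45%) positive with CellSearch, which this trial does not use, and a pilot of 20 patients with about 47% having at least 1 CTC per 7.5 mL, whose assay is not named.

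**The concern.** A detectable/undetectable comparison needs a reasonable number of patients in each group. The only detection data in the documents that are expressly from this assay are 5 positive out of 5. If most of the 25 patients are also positive, one row of the two-by-two table will be very small or empty, and Fisher's test will be unable to show an association however strong it is. The graded information that could show one, the count itself, is collected but not used at baseline.

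What is at stake is the baseline half of an exploratory objective. If the cutpoint has to be rethought after the counts are known, it also becomes data-driven.

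**Working it through.** **1. The plan's own figures.** No power, alpha or expected group size is given for the CTC test. I use two-sided 0.05 as an assumption. The primary test (9.2.1) has n = 25, 25% v 50% at 6 months, one-sided 10%, stated power 88%. A rule of at least 10 successes in 25 gives alpha 7.1% and power 88.5%, so the stated figure reproduces. It also supplies the outcome margin: 0.25 × 25 ≈ 6 patients reaching 6 months under the null, and 0.50 × 25 = 12.5, so 12 or 13, under the alternative.

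**2. What 5 of 5 says about detection.** The exact 95% lower limit is 0.025^(1/5) = 0.478.

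**3. Predicted number undetectable, K, among 25.** With a Beta(a, b) posterior for the detection rate, P(K = k) = C(25, k) · B(b + k, a + 25 − k) / B(a, b). The posterior is Beta(6, 1) from a uniform prior and Beta(5.5, 0.5) from a Jeffreys prior. For example, the uniform prior gives P(K = 0) = 6/31 = 0.194.

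| Undetectable among 25 | Uniform prior | Jeffreys prior |
|---|---|---|
| none | 19% | 42% |
| at most 1 | 35% | 59% |
| at most 2 | 49% | 70% |
| at most 3 | 60% | 78% |

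**4. Smallest attainable Fisher p.** The most extreme table puts all k undetectable patients on one side of 6 months. If m of 25 reach 6 months, its probability is C(m, k)/C(25, k), which here is also the two-sided p. For m = 13 the minimum comes from the 12 who do not reach 6 months, so the values are the same as for m = 12.

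| k undetectable | m = 12 or 13 | m = 6 |
|---|---|---|
| 1 | 12/25 = 0.48 | 6/25 = 0.24 |
| 2 | 66/300 = 0.22 | 15/300 = 0.05 |
| 3 | 220/2300 = 0.096 | 20/2300 = 0.0087 |
| 4 | 495/12650 = 0.039 | 0.0012 |

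At the design alternative at least 4 undetectable patients are needed for p < 0.05. At the design null at least 3 are needed.

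**5. Illustration of power.** Assume 6-month TTP rates of 80% v 20% between the two CTC groups; these rates are not from the documents. Fisher's test on a median split (12 v 13) has 89% power. The planned split, averaged over the group sizes predicted in step 3, has 38% (uniform) or 23% (Jeffreys). By true detection rate, the planned split has 86% power at 47% detection, 61% at 80%, 34% at 90% and 14% at 95%. With 75% v 25%, the median split has 73% and the planned split 15–27%.

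**6. A Cox model on the log count.** Approximate power is P(Z > 1.96 − √events × ln HR), with HR per SD of log count. At HR 2, 15 events give √15 × 0.693 − 1.96 = 0.72, so 77%; 20 events give 87%. At HR 1.5 the figures are 35% and 44%. The HRs and event numbers are assumptions.

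**The case against.** Several stronger readings are tempting, and the documents do not support them.

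- **That the test will probably have no contrast at all.** Five patients cannot carry that. An empty undetectable group has a predicted chance of 19–42%, and becomes more likely than not only if true detection exceeds about 97% (0.973^25 = 0.50). If detection were near 47%, the planned split would do almost as well as a median split. A single empty cell is also no obstacle to Fisher's test; only an empty row is.
- **That every phase I patient was detectable.** Section 1.4.2 reports 5 expansion patients, while the trial enrolled 25 (1.2.3.1). It also speaks of circulating epithelial cells, and 7.3.1 describes credentialing such cells as tumor cells. A stricter definition of detectable would leave more patients undetectable, but 9.4.4 gives no definition.
- **That the 47% pilot figure is certainly from another assay.** The context suggests it, but the assay is not named, and the 7.5 mL volume does not settle it because 7.3.1 uses tubes of about that size.
- **That the whole CTC objective fails.** The change analysis uses the direction of change in the counts and does not need an undetectable group. The objective says TTP and/or OS, so omitting OS leaves a named outcome without an analysis but is not a strict contradiction.
- **That a count-based analysis would be well powered.** That depends on the assumed HR (step 6). The case for using the count does not rest on it.

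What stands of the objection is that the problem is one of likelihood, it concerns the baseline test only, and no trial decision depends on it.

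**Conclusion.** The concern holds for the baseline comparison. On the documents' own evidence, that test is more likely than not to be uninformative at the design alternative: the chance of 3 or fewer undetectable among 25 is 60–78%, and in that range p < 0.05 is out of reach whatever the data show. At the design null the corresponding chance, of 2 or fewer, is 49–70%.

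This rests on treating the 5 phase I patients as exchangeable with the present ones, on a uniform or Jeffreys prior, on baseline results for all 25 patients, on two-sided 0.05, and on detectable meaning the same as in 1.4.2. The endpoint is exploratory, so this is a worthwhile refinement and not a threat to the trial's conclusions.

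**What to change.** In 9.4.4, make the baseline count the prespecified analysis: log(count + 1) as a continuous covariate in a univariate Cox model, fitted separately for TTP and OS, reporting the hazard ratio with its 95% confidence interval. Show Kaplan-Meier curves by a median split for display. Define detectable, and keep the detectable/undetectable table against 6-month TTP as description only. The change analysis can stay as written.

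Section 9.4.4 already uses univariate Cox models for the mTOR markers, so no new method is introduced. A time-to-event model also keeps patients censored before 6 months, whom a yes/no table at 6 months cannot classify.

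The cost is SAP wording and a little more analysis work, with no extra sample, visit or assay. The price in assumptions is a log-linear effect of the count. The change should be made before the counts are seen.

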
Efficacy Assessments (continued)
	
Exploratory Endpoints CTC will be enumerated in peripheral blood at baseline and after 1 and 2 cycles of therapy to evaluate for any relationship between baseline levels and change in levels with median TTP and/or OS; baseline level of CTC will be compared to proportion with TTP at 6 months to determine if there is an association using Fisher’s Exact tests. Change in CTC levels (increase or decrease) after 1 and 2 cycles will be compared to TTP to determine if there is an association using Fisher’s Exact tests. In all patients with active or chronic HBV infection, changes in HBV DNA quantitative by PCR will be characterized using descriptive statistics to calculate the proportion of patients with an increase or reactivation in viral load while on protocol therapy.

Unique Aspects of this Study
	
This Phase II trial is being developed following completion of a Phase I study of the combination of temsirolimus and sorafenib in 25 first-line therapy patients with advanced hepatocellular carcinoma (December 2009 through April 2012). The MTD and recommended phase II dose (RP2D) of the combination was temsirolimus 10 mg IV weekly plus sorafenib 200 mg PO BID.

List of Abbreviations

AE	adverse event
ALP	alkaline phosphatase
ALT	alanine aminotransferase
ANC	absolute neutrophil count
AST	aspartate aminotransferase
ATC	Anatomical Therapeutic Chemical (Classification System)
AUC	area under the curve
BUN	blood urea nitrogen
CBC	complete blood cell (count)
CHR	Committee on Human Research (UCSF IRB)
CR	complete response
CRC	Clinical Research Coordinator
CRF	case report form
CSF	cerebral spinal fluid
CT	computerized tomography
CTCEA	Common Terminology Criteria for Adverse Events
CTEP	Cancer Therapy Evaluation Program
CTMS	Clinical Trial Management System
DFS	disease-free survival
DLT	dose limiting toxicity
DSMC	Data and Safety Monitoring Committee
DSMP	Data and Safety Monitoring Plan
ECOG	Eastern Cooperative Oncology Group
FCBP	female of childbearing potential
FDA	Food and Drug Administration
GCP	Good Clinical Practice
HBeAg	Hepatitis B “e” antigen
HBV	Hepatitis B virus
HCC	Hepatocellular carcinoma
HCT	Hematocrit
HCV	Hepatitis C virus
HDFCCC	Helen Diller Family Comprehensive Cancer Center
HGB	Hemoglobin
HIV	human immunodeficiency virus
ICH	International Conference on Harmonization

List of Abbreviations

IND	investigational new drug application
IP	investigational product
IRB	Institutional Review Board

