9.4.3 Analysis of Secondary Endpoints

Response rates will be summarized and presented with 95% exact binomial confidence intervals. The comparison of response rates will use Fisher's exact test.

Kaplan-Meier methods will be used to summarize time-to-event outcomes including the primary endpoint (median TTP) and secondary endpoints (PFS, TTF, OS). Proportions of patients with TTP, PFS, and TTF equal to or exceeding 6 months will be calculated with 95% confidence intervals. Tumor response by RECIST 1.1 measurements will be presented descriptively for the study cohort.

- **AFP Response:** Baseline levels (high or low) will be compared to absolute TTP to determine if there is an association using Fisher's Exact tests or by Wilcoxon Rank-Sum test. Changes in levels on therapy with temsirolimus and sorafenib will be measured as an increase by $\geq 50\%$ from baseline, stable value within 50% of baseline, or decrease by $\geq 50\%$ from baseline. The change in level will be used to evaluate the predictive value for TTP. Fisher's Exact tests will be used to test for significance. Kaplan-Meier methods and Log-rank tests will also be used to estimate TTP based on the AFP.

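### On-treatment CTC change is scored only by its sign, with no minimum change and no rule for unchanged counts, although the assay gives a count that a rank test could use at no extra cost

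*Combined protocol and SAP*

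**What the plan says.** Section 9.4.4 sets the on-treatment analysis: "Change in CTC levels (increase or decrease) after 1 and 2 cycles will be compared to proportion with TTP at 6 months", using Fisher's exact test. The Abstract (Exploratory Endpoints) has the same two classes but names TTP itself as the outcome: "Change in CTC levels (increase or decrease) after 1 and 2 cycles will be compared to TTP".

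Section 7.3.1 gives the measurement scale: "The result of the CEpiC assay is the count of positive CEpiCs per milliliter of peripheral blood with associated imagery". Each tube holds about 7.5 mL, and samples are taken at baseline and on Day 1 of Cycles 2 and 3.

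Two other serial markers are treated differently:

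- **AFP (section 9.4.3):** three classes cut at a 50% change, with a middle class described as "stable value within 50% of baseline".
- **HBV DNA (section 9.4.4):** a rise of at least 50%, or conversion to detectable, set against an unchanged class.

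For CTC the documents give no minimum change, no assay precision and no rule for an unchanged count. They state no significance level, effect size or power for this test.

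**The concern.** The dividing line between the two classes is the patient's own single baseline count. A fall from 5 cells to 4 scores the same as a fall from 50 to 0, although the assay shows the difference. A patient with the same count twice belongs to neither class. Someone must then decide after the data are in whether to exclude that patient or to pool the patient with one class, and each choice gives a different 2x2 table.

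At stake is whether about 25 patients with paired counts can show a relation between CTC change and TTP. Sign-only scoring mixes counting noise into both classes. It also cannot separate groups that move in the same direction by different amounts.

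**Working it through.** **Plan's own figure.** None is stated for the CTC change test, so there is none to reproduce.

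**Inputs from the documents.** 25 evaluable patients (section 3.2); two classes, increase or decrease (section 9.4.4); a count as the assay result (section 7.3.1). On expected levels, section 1.4.2 offers only a CellSearch pilot of 20 patients, with "47% to have ≥ 1 CTC/7.5 mL detected" and about 30% with at least 3, and for the assay used here, "all 5 had detectable circulating epithelial cells by the slide-based CEpiC assay". Neither source gives a mean count.

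**Assumptions.** Poisson counts per sample, with means of 1, 3, 10 and 50 to show the range.

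**Step 1: no true change.** For two independent Poisson counts with the same mean μ, P(tie) = e^(−2μ)·I₀(2μ), where I₀ is the modified Bessel function, and P(decrease) = (1 − P(tie))/2.

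| Mean count | Tie (fits neither class) | Scored decrease | Scored increase |
|---|---|---|---|
| 1 | 30.8% | 34.6% | 34.6% |
| 3 | 16.7% | 41.7% | 41.7% |
| 10 | 9.0% | 45.5% | 45.5% |
| 50 | 4.0% | 48.0% | 48.0% |

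Below a mean of 1, the decrease share falls and ties grow. The mean that gives 47% detectable solves 1 − e^(−μ) = 0.47, so μ = 0.635, with 40.6% ties and 29.7% decreases. A single Poisson mean does not fit the pilot, however: at 0.635 the share with 3 or more would be 1 − e^(−0.635)(1 + 0.635 + 0.635²/2) = 2.7%, against about 30% reported. Counts therefore vary between patients, and step 2 allows for this.

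**Step 2: power.** Simulated trials of 25 patients, half of them with TTP of at least 6 months and all with known 6-month status. Between-patient spread is gamma with shape 1, there is Poisson noise at both visits, and the level is two-sided 5%. The sign-based Fisher test is compared with a Wilcoxon rank-sum test on log((count + 0.5)/(baseline + 0.5)). A range for Fisher covers ties dropped, or pooled with either class; a single figure is for ties dropped.

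| True change in the two groups | Mean | Fisher on sign | Rank test on log ratio |
|---|---|---|---|
| 0.3x v stable | 3 | about 30-34% | 56% |
| 0.3x v stable | 10 | 53-59% | 92% |
| Stable v 3x | 3 | 42-67% | 78% |
| Stable v 3x | 10 | 71% | 97% |
| 0.5x v 1.5x | 3 | 53% | 62% |
| 0.5x v 1.5x | 10 | 92% | 94% |

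With no effect, the rank test rejects in about 4-6% of trials and Fisher with ties dropped in about 3%.

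**Step 3: would an AFP-style 50% cut do instead?** This check assumes 80% v 10% reaching 6 months, n = 25 and two-sided 10%, where perfect classification gives 98% power. At mean 10, true quartering against no change gives 53% with the sign rule (ties dropped) and 87% with a class for a fall of at least 50%. True halving against true doubling gives 93% with the sign rule and 64% with the cut. A cut helps in one case and hurts in the other.

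**The case against.** The strongest case for leaving the text alone is that a sign rule is pre-specified and needs no cutpoint. That is defensible for a new assay without documented precision or a validated threshold. The counts are kept and can still be reported. Part of the power gap comes from Fisher's conservatism, not from scoring by sign. When groups move in opposite directions, which is the pattern a sign rule looks for, little is lost at moderate or high counts.

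Much of this stands, and it limits the point. Four stronger readings are tempting, and the documents support none of them:

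- **Noise makes 35-48% of this trial's patients decreasers.** That range needs Poisson noise, mean counts of 1 to 50 and no true change. The documents give none of these.
- **Ties are dropped.** The plan does not say so. Their handling is undefined, and pooling can move Fisher's power either way.
- **The test loses much of its power in general.** The loss depends on the counts and on what the other group does.
- **This test decides whether CTC change is pursued as a marker.** Sections 2.3 and 9.1.4 make it exploratory, with no decision rule. The go-forward criterion in section 1.3 is median TTP.

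The objection does not remove the gap for unchanged counts. Nor does it rescue the sign test on power: the rank test at least matched Fisher in every effect scenario run, under each way of handling ties, with null rejection near 5%. It needs no cutpoint either, and section 9.4.3 already lists it for baseline AFP against TTP.

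**Conclusion.** The point holds as a low-severity, cheap improvement. The text gap is certain: there are two classes, no minimum change, and no place for an unchanged count, where AFP and HBV DNA have both a threshold and a stable or unchanged class. The size is conditional on assumed gamma-Poisson counts, 25 patients with paired samples and known 6-month status, and a two-sided 5% level that the plan does not set; the neighbouring Fisher calculation in section 9.4.4 uses two-sided 10%. Under those assumptions the power cost of sign scoring is clear when one group is stable. At mean 10 it is between 92 − 59 = 33 and 92 − 53 = 39 percentage points for a fall to 0.3 times baseline. It is about 2 points at the same mean for opposite movements of 0.5x and 1.5x. No error in a stated power or sample size follows, because none is stated for this test.

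**What to change.** In section 9.4.4 and the Abstract, replace the increase-or-decrease classes with the log ratio of on-treatment to baseline count, log((count + 0.5)/(baseline + 0.5)), after 1 and after 2 cycles. Compare it between patients with and without TTP of at least 6 months by Wilcoxon rank-sum test. Unchanged counts, including 0 to 0, then enter as zero change.

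State the scale. The constant 0.5 is meant for cells counted per sample. On the reported per-mL scale it would equal 0.5 × 7.5 = 3.75 cells per tube, so a per-mL analysis needs a rescaled constant, for example 0.5/7.5 ≈ 0.067 per mL.

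The increase/decrease table may stay as a descriptive display, with unchanged counts shown in their own row.

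Cost: a few words in two places, with no new samples or assays. The downside is that the result is slightly less simple to present than a 2x2 table.

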9.1.3 Secondary Endpoints

1. Response rate (RR) will be measured by RECIST version 1.1.

2. Median PFS will be calculated in months from date of first dose of protocol therapy to date of study removal for documented radiographic and/or clinical disease progression or death from any cause. For patients removed from study for other reasons than progression or death, PFS will be censored at the date last known to be progression-free.
3. Median OS for all enrolled patients who receive at least one dose of protocol therapy will be calculated from date of first dose of protocol therapy until date of death, using chart review and/or follow up phone calls to determine date of death in patients after removal from study. The survival of patients still alive after 5 years of follow up post study discontinuation will be censored.
4. TTF will be measured from date of first dose of protocol therapy to date of removal from study for progression, death, or toxicity. For patients removed from study for other reasons (such as noncompliance or withdrawal of consent), TTF will be censored at the date of study discontinuation.
5. In patients with baseline AFP ≥ 20 ng/mL, AFP response will be measured by the percent change from baseline value to the value at the time of best AFP response. The proportion of $\geq 50\%$ decline from baseline will be measured. The change in AFP will also be examined for association with absolute TTP and best response.
6. Toxicity will be measured using Common Terminology Criteria for Adverse Events (CTCAE) version 4.0. The frequency of dose reduction, treatment delays, and discontinuation for lack of tolerability will be quantified.

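### Section 9.4.4 tests mTOR markers against AFP decline only as yes/no cuts; testing the uncut Cycle 2 Day 1 change would gain power, mainly for moderate effects

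*Combined protocol and SAP*

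**What the plan says.** Section 9.4.4 first reduces the tissue markers to high or low: "Due to possible limited specimen quantity, IHC outcomes will be dichotomized". The AFP outcome is then also reduced. "The association between each protein and the two binary coding schemes for AFP decline", at least 50% or at least 20%, "on C2D1 will be tested using Fisher's exact test". The composite variable for overall pathway activation is examined by the same methods.

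The power statement reads "For each test of association with AFP change, based upon Fisher's exact test large differences can be detected". Its example is "10% among 7 patients with marker-low, 80% among 8 patients with marker-low", with 81% power at a two-sided alpha of 10%. The same section says the sample is too small to test TTP, OS or other clinical endpoints by pathway status. It expects at least 25 cases with usable tissue, and in practice 40 to 45, with "60% evaluable for AFP response on C2D1", that is, at least 15.

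AFP is drawn on Cycle 1 Day 1 (6.1.2.1) and on Day 1 of every later cycle (6.1.2.2). The secondary endpoint in 9.1.3 is related but different: "AFP response will be measured by the percent change from baseline value to the value at the time of best AFP response".

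**The concern.** A yes/no cut keeps which side of the threshold a patient falls on and discards the size of the AFP change. With as few as 15 patients that is a real loss, and it falls on the one marker-outcome comparison for which the plan claims usable power. The plan explains why the tissue markers are dichotomised but gives no reason in 9.4.4 for testing AFP only in dichotomised form. The Wilcoxon test in 9.4.3 relates baseline AFP to TTP and does not fill the gap.

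If moderate marker effects exist, the planned tests are likely to miss them. Two codings also double the tests: four proteins plus the composite make 5 x 2 = 10 Fisher tests.

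**Working it through.** **Inputs from 9.4.4.** Groups of 7 and 8; decline rates 10% and 80%; two-sided alpha 10%; stated power 81%; at least 25 cases, 40-45 expected, 60% evaluable for AFP. Both groups in the example are labelled marker-low. One is presumably marker-high, and the arithmetic is unaffected.

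**Assumption not in the documents.** No distribution or SD for AFP change is given. The base case takes log AFP ratio as normal with equal SD in both marker groups. The Wilcoxon result is the same on any monotone scale.

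**Step 1: the plan's own figure.** Power = sum over a = 0..7 and b = 0..8 of Bin(a; 7, 0.10) x Bin(b; 8, 0.80) x 1{Fisher p(a, b) <= 0.10}.

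- One-sided p doubled (5% in the tail): 81.4%, which reproduces the stated 81%.
- Usual two-sided Fisher p: 83.6%.

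The Fisher figures in Steps 4 and 5 use the usual two-sided p unless a range is shown for both conventions.

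**Step 2: the same example, uncut.** Rates of 10% and 80% below one cut imply a shift of z(0.80) - z(0.10) = 0.842 + 1.282 = 2.12 SD. With 7 v 8 patients the exact Wilcoxon test at two-sided 10% has actual size 9.4%. Simulation of 200,000 trials gives 98.0% power; the t test gives 98.7%.

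**Step 3: how far the 98% depends on assumptions.** In each row the rates at the cut stay at 10% and 80%.

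| Condition | Wilcoxon power |
|---|---|
| Normal, equal SD | 98.0% |
| Logistic | 96.6% |
| Laplace | 93.9% |
| t, 3 df | 93.5% |
| t, 2 df | 90.2% |
| Normal, second group's SD x 0.5 / x 2 / x 3 | 97.3% / 94.0% / 88.5% |
| Size of change uninformative beyond the cut | 80.2% (no gain) |
| Normal, equal SD, size held to 4.0% / 5.4% | 94.3% / 95.9% |

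The last row matters because Fisher's actual size at 7 v 8 is at most 4.6%. Part of the gap between 81-84% and 98% is therefore alpha that Fisher's test leaves unused, but most of it remains at matched size.

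**Step 4: smaller effects, 7 v 8, normal equal-SD shift.**

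| Rates | Fisher | Wilcoxon |
|---|---|---|
| 10% v 60% | 53% | 85% |
| 20% v 70% | 45-48% | 77% |

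**Step 5: the expected sample.** The floor is 0.60 x 25 = 15. The expected numbers are 0.60 x 40 = 24 to 0.60 x 45 = 27.

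| Groups and rates | Fisher | Wilcoxon |
|---|---|---|
| 11 v 13 to 13 v 14, 10% v 80% | 97-99% | over 99% |
| 12 v 12, 10% v 60% | 79% | 97% |

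At that size the plan's example is well powered under either test. The gain that survives is for moderate effects.

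**The case against.** The strongest reply is that these are established responder definitions in an exploratory analysis, and that the plan already says only large differences are detectable. Much of that stands.

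- **Basis of the cuts.** A reader might infer that 50% and 20% are arbitrary. They are not. Section 1.4.1 cites a study in which a decline of at least 20% separated survival (13.5 v 5.6 months). The 50% cut was used to report the phase I trial (1.2.3.1, 8 of 16) and is part of the AFP endpoint in 2.4.2 and 9.1.3. That supports reporting both rates; it does not require testing only on them.
- **Selective reporting.** A reader might infer that two codings let the team pick the better one. Both are prespecified, and 9.4.4 says the results of each test will be summarised. The multiplicity is also modest: counting either cut as positive raises the null rejection rate per marker from about 4-5% to about 7-8%, still under 10%.
- **Two cuts recover the loss.** Only in part. At 7 v 8, with the example's rates placed at the 50% cut and an assumed log-AFP SD of 0.5 to 1.2, either-cut power is 91-93% for 10% v 80% and 67-73% for 10% v 60%. One Wilcoxon test gives 98% and 85% under the same normal model.
- **The uncut variable.** A reader might infer that 9.1.3 already defines it. That section concerns best AFP response, not C2D1. The C2D1 change can be computed from scheduled draws but has to be defined.

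**Conclusion.** The point holds as a modest one. Testing the markers only on cut AFP decline gives up power that the scheduled data could supply. At the minimum of 15 patients the comparison is about 81-84% v 98% for 10% v 80%, and 53% v 85% for 10% v 60%, under an equal-SD normal shift in log AFP ratio that the plan does not give.

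An unconditional claim that power rises to 98% is not supported. The shapes tried give about 88-98%, matched size gives 94-96%, and the gain is nil if the size of the change adds nothing to the cut. At the expected 24-27 patients the benefit is confined to moderate effects.

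The analysis is exploratory and pools data from the earlier study. The primary endpoint, safety monitoring and the decision on a randomised trial are untouched. This is a cheap improvement to consider.

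**What to change.** In 9.4.4:

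1. Define the variable as the log of C2D1 AFP over baseline AFP.
2. Make one Wilcoxon rank-sum test of it the test for each marker and for the composite, which is 5 tests in place of 10. Report the Hodges-Lehmann shift with a 90% CI, to match the two-sided 10% level.
3. Keep the proportions with at least 50% and at least 20% decline as descriptive summaries with confidence intervals, so comparison with phase I and the cited study is preserved.
4. Restate the power sentence for this test with its distributional assumption, and correct the duplicated marker-low label.

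The cost is wording only: no new visits, samples or data. The drawback is that a shift in log AFP is less familiar to clinical readers than a responder rate, which is why both rates should still be shown.
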